5.0 STUDY PROCEDURES

5.1 Screening/Baseline Procedures

Assessments performed exclusively to determine eligibility for this study will be done only after obtaining informed consent. Assessments performed for clinical indications (not exclusively to determine study eligibility) may be used for baseline values even if the studies were done before signed informed consent was obtained.

- 5.1.1 All screening procedures must be performed within 14 days prior to Course 1 Day 1 unless otherwise stated.
- 5.1.2 Screening medical history, including complete medical and surgical history, history of infections, and MRI of the brain and spine
- 5.1.3 Demographics, including age, gender, race, ethnicity
- 5.1.4 Review subject eligibility criteria
- 5.1.5 Review previous and concomitant medications
- 5.1.6 Physical exam including vital signs (temperature, pulse, respirations, blood pressure, pulse oxygenation), height, weight, neurologic exam
- 5.1.7 Performance status, (Lansky Play Scale for children \leq 10 years of age, Karnofsky Performance Level for patients $>$ 10 years of age.)
- 5.1.8 Adverse event assessment: Baseline adverse events will be assessed. See section 6 for Adverse Event monitoring and reporting.

- 5.1.9 Hematology: CBC with differential
- 5.1.10 PT/PTT/INR
- 5.1.11 Serum chemistries to include: alkaline phosphatase, ALT, AST, total bilirubin, calcium, phosphorus, BUN, creatinine, total protein, albumin, fasting glucose, potassium, sodium, chloride, bicarbonate, uric acid, LDH, fasting lipid panel (LDL, total cholesterol, triglycerides)
- 5.1.12 Hepatitis serology, including HBsAg, HBsAb, HBcAb, Hep C RNA for patients at risk of hepatitis as defined in Section 3.2.14.
- 5.1.13 Pregnancy test (for females of child bearing potential), See section 3.2.13 for definition.
- 5.1.14 Informed Consent
- 5.1.15 Tumor assessment:
 - 5.1.15.1Central Pathology Review
 - 5.1.15.2Correlative biology studies (12 unstained FFPE slides)

5.2 Procedures During Treatment

- 5.2.1 **Monthly (+/- 7 days):**
 - Physical exam (including neurologic exam), vital signs, performance status
 - Pulse Oximetry
 - CBC with differential
 - Serum Chemistries to include: alkaline phosphatase, ALT, AST, total bilirubin, calcium, phosphorus, BUN, creatinine, total protein, albumin, fasting glucose, potassium, sodium, chloride, bicarbonate, uric acid, LDH, fasting lipid panel (LDL, total cholesterol, triglycerides)
 - PT/PTT/INR
 - Urine pregnancy test for females of childbearing potential (Section 3.2.12)
 - AE Assessment
 - Review of Concomitant Medications
 - Drug Accountability Review
 - Everolimus trough levels will be tested 2 weeks after starting protocol therapy. Repeat testing may be required if there are dose adjustments or other parameters met as defined in Section 5.2.4.
- 5.2.2 **Assessment of Tumor Response:**
 - MRI of the brain and spine: MRI of the brain and spine should be performed every other month for the first year, every third month for the second year, and whenever clinically indicated. Specifically, prior to courses 3, 5, 7, 9, 11, 13, 16, 19, 22, and then at the end of treatment (after course 24). Note: MRI should be completed within 7 days *before* the start of the indicated cycles.
 - Lumbar puncture for cytology: Not required, but to be performed as clinically indicated
- 5.2.3 **Within 30 days after treatment termination:**
 - Physical exam (including neurologic exam), vital signs, performance status
 - CBC with differential
 - Serum Chemistries to include: alkaline phosphatase, ALT, AST, total bilirubin, calcium, phosphorus, BUN, creatinine, total protein, albumin, fasting glucose,

potassium, sodium, chloride, bicarbonate, uric acid, LDH, fasting lipid panel (LDL, total cholesterol, triglycerides).

- PT/PTT/INR
- Urine pregnancy test for females of childbearing potential (Section 3.2.12)
- Hepatitis serology, including HBsAg, HBsAb, HBcAb, Hep C RNA for patients at risk of hepatitis as defined in Section 3.2.14.
- AE Assessment
- Review of Concomitant Medications
- Drug Accountability Review

5.2.4 Pharmacokinetic Drug Monitoring and Adjustments:

The target drug trough level of Everolimus is 5 – 15 ng/ml.

- Everolimus trough levels will be assessed 2 weeks (+/- 4 days) after starting drug. If the level is outside of the target range, then the dose should be adjusted to achieve a trough level of 5 – 15 ng/ml. Trough levels should be assessed within one hour before taking the daily dose.
- Whenever any dose adjustment of Everolimus occurs, trough levels should be reassessed two weeks (+/- 4 days) following the adjustment to ensure that the new dose achieves the target drug trough level of 5-15 ng/ml.
- Furthermore, Everolimus trough levels should be assessed 2 weeks (+/- 4 days) following the starting, ending, or changing of the dose of inducers or inhibitors of CYP3A4 or P-glycoprotein.

5.3 Follow-up Procedures

Patients will be followed for survival after completion of (or early withdrawal from) study treatment or death.

Adverse Events and concomitant medication monitoring should be continued for at least 30 days following the last dose of study treatment.

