2.2 Secondary Objectives

- 2.2.1 Determine the duration of response, progression free survival (PFS) and event free survival (EFS) following treatment with everolimus for children with recurrent or progressive ependymomas.
- 2.2.2 Determine safety and tolerability of everolimus among children with recurrent or progressive ependymomas.
- 2.2.3 Descriptive analysis and correlation of response rate to biological markers of mTOR pathway activation, including phosphorylated S6^{235/236}, phosphorylated S6^{240/244}, phosphorylated PRAS40 (pT246), phosphorylated 4EBP1, phosphorylated P70^{S6K}, and PTEN expression.

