4.9 Duration of Follow Up

Patients will be followed after removal from treatment or until death, whichever occurs first. Follow-up for survival will occur by the treating oncologist and will be communicated to the PI or designee at 6-month intervals by phone or medical record review. Patients removed from treatment for unacceptable adverse events will be followed until resolution or stabilization of the adverse event.

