6.1.12 Progression-Free Survival

Progression-free survival (PFS) is defined as the duration of time from start of treatment to time of progression.

6.1.13 **Event-Free Survival**

Event-Free Survival (EFS) is defined as the duration of time from start of treatment to: (1) disease progression; (2) second malignant neoplasm; (3) death regardless of cause; or (4) date of last contact, whichever comes first.

6.2 **Safety/tolerability**

Analyses will be performed for all patients having received at least one dose of study drug. The study will use the CTCAE version 4.03 (download: <http://ctep.cancer.gov/reporting/ctc.html>) for adverse event reporting.

7.0 **ADVERSE EVENTS**

7.1 **Experimental Therapy**

7.1.1

7.2 **Adverse Event Monitoring**

Adverse event data collection and reporting, which are required as part of every clinical trial, are done to ensure the safety of subjects enrolled in the studies as well as those who will enroll in future studies using similar agents. Adverse events are reported in a routine manner at scheduled times during a trial. Additionally, certain adverse events must be reported in an expedited manner to allow for optimal monitoring of the subject's safety and care. Adverse events not requiring expedited reporting will be entered into the eCRF on a monthly basis.

All subjects experiencing an adverse event, regardless of its relationship to study drug, will be monitored until:

- the adverse event resolves or the symptoms or signs that constitute the adverse event return to baseline;
- any abnormal laboratory values have returned to baseline;
- there is a satisfactory explanation other than the study drug for the changes observed; or
- death.

7.2.1 **Definitions**

An adverse event is defined as any untoward or unfavorable medical occurrence in a human research study participant, including any abnormal sign (for example, abnormal physical exam or laboratory finding), symptom, clinical event, or disease, temporarily associated with the subject's participation in the research, whether or not it is considered related to the subject's participation in the research.

Adverse events encompass clinical, physical and psychological harms. Adverse events occur most commonly in the context of biomedical research, although on occasion, they can occur in the context of social and behavioral research. Adverse events may be expected or unexpected.

Severity

Adverse events will be graded by a numerical score according to the defined NCI

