9.2 Sample Size and Accrual

Simon's two-stage optimal design³⁵ is used to compute the number of patients to be recruited for this phase II trial. The null hypothesis that the true objective response rate (ORR) is 10% will be tested against a one-sided alternative. In the first stage, 7 patients will be accrued. If there is no ORR seen in these 7 patients, the study will be stopped.

Otherwise, 11 additional patients will be accrued for a total of 18 patients. The null hypothesis will be rejected if 4 or more ORRs are observed in 18 patients. This design yields a type I error rate of 10% and power of 80% when the true ORR is 30%. It is expected that the accrual will be completed in 2 years since 9 patients are expected to be recruited in a year.

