- 12 Lumbar puncture for cytology is optional but may be performed if clinically indicated.
- 13 The End of Treatment Visit should be completed within 30 days of treatment termination.
- 14 Adverse event and concomitant medication monitoring should be continued for at least 30 days following the last dose of study treatment
- 15 Survival follow up will be completed by phone or medical record review.

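### After the end-of-treatment visit, progression and second malignancy are not systematically collected for children who stop everolimus without progression, so EFS, PFS and duration of response lose information and can be biased

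*Combined protocol and SAP*

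**What the plan says.** **What has to be estimated.** Section 2.2.1 sets the secondary objective: "Determine the duration of response, progression free survival (PFS) and event free survival (EFS) following treatment with everolimus". Section 6.1.12 runs PFS from start of treatment to progression and mentions neither death nor censoring. Section 6.1.13 ends EFS at "1) disease progression; (2) second malignant neoplasm; (3) death regardless of cause", and then lists the date of last contact as a fourth end point. Section 6.1.11 ends duration of response at objectively documented recurrence or progression. None of these definitions stops at the last dose. Section 9.3 applies Kaplan-Meier to all three and gives no censoring rule.

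**What is collected after treatment.** Section 5.3: "Patients will be followed for survival after completion of (or early withdrawal from) study treatment or death". Section 4.9: "Follow-up for survival will occur by the treating oncologist and will be communicated to the PI or designee at 6-month intervals", by phone or record review. In Appendix II the long-term column has one mark, for survival and other treatment, and footnote 15 adds: "Survival follow up will be completed by phone or medical record review".

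**Imaging.** MRIs are scheduled before courses 3 to 22 and at end of treatment. For a child who stops early the last scan is unclear. Appendix II marks imaging at the end-of-treatment visit, but footnote 11 ties that scan to completion of course 24, and the Section 5.2.3 list of procedures within 30 days has no MRI.

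**The concern.** A child can leave treatment progression-free because of toxicity, withdrawal or physician judgment (Section 5.5), or by completing two years (Sections 4.5 and 4.8). For that child the next event that all three endpoints need is progression, and the follow-up schedule does not ask for it. Nor does it ask about second malignancy, a named EFS event.

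Suppose a child stops at month 4, progresses at month 6 and dies at month 16. The scheduled contacts would give the death date but need not give the progression date. EFS might then be recorded at month 16 instead of month 6, or censored at month 4, and the plan does not say which. Children who complete treatment without progression matter most for duration of response, because their later progression dates determine how long the responses last.

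**Working it through.** **1. The plan's own figure.** The only computed figure is the two-stage design in Section 9.2: "The null hypothesis that the true objective response rate (ORR) is 10% will be tested against a one-sided alternative". Stage 1 takes 7 patients and stage 2 adds 11, giving 18. The study stops if none of the 7 respond, and the null is rejected at 4 or more responses in 18. With X ~ Bin(7, p) and Y ~ Bin(11, p):

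P(reject) = Σ over x = 1 to 7 of P(X = x) · P(Y ≥ 4 − x)

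This gives 0.0893 at p = 0.10 and 0.8000 at p = 0.30, so the stated 10% (as a ceiling) and 80% are reproduced. No term uses a post-treatment progression date. The plan states no figure for EFS, PFS or duration of response.

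**2. EFS if deaths count but off-treatment progressions are unseen.** These inputs are assumptions, not document figures:
- exponential time to progression, median 4 months (range 3 to 6): λ = ln 2/4 = 0.1733 per month
- exponential survival after progression, median 10 months: μ = ln 2/10 = 0.0693 per month
- a proportion q of children assigned a stop time uniform over months 0 to 6
- progression hazard unchanged by stopping.

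True 12-month EFS = 2^(−12/4) = 12.5%. Recorded EFS is higher because some children progress off treatment before month 12 and are still alive then. With d = λ − μ = 0.1040:

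excess = q · (λ/d) · e^(−12μ) · [(1 − e^(−6d))/(6d) − e^(−12d)]
= q · 1.667 · 0.4353 · (0.7440 − 0.2872) = q · 0.331

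The share actually stopping before progression is q · (1 − e^(−6λ))/(6λ) = q · 0.622.

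| q assigned a stop | Stop before progression | Recorded 12-month EFS | True | Excess |
|---|---|---|---|---|
| 5% | 3.1% | 14.2% | 12.5% | +1.7 |
| 16.7% (3/18) | 10.4% | 18.0% | 12.5% | +5.5 |
| 27.8% (5/18) | 17.3% | 21.7% | 12.5% | +9.2 |

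At q = 27.8%, a median of 3 months gives 14.8% against 6.3%, and a median of 6 months gives about 34% against 25%.

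**3. The same model, censoring at stop.** The 12-month Kaplan-Meier estimate is 12.5% against a true 12.5%, so there is no bias. The result in step 2 depends on the handling rule as well as on the missing data.

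**4. Alternative rules, with informative stopping allowed.** This is a separate simulation of 40,000 children per scenario. Assumed inputs: median time to progression 4, 6 or 12 months; 15% or 30% stopping for other reasons by 12 months; median survival after progression 9 months; progression hazard unchanged or doubled after stopping. The 12-month results for median 6 months and 30% stopping are:

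| Handling of children who stop | Hazard unchanged | Hazard doubled |
|---|---|---|
| Full follow-up (truth) | 25.1% | 21.3% |
| Censored at stop | 24.9% (−0.2) | 25.0% (+3.7) |
| Deaths seen, progressions unseen | 31.6% (+6.5) | 30.1% (+8.8) |
| Stop taken as last contact and counted as an event | 17.4% (−7.7) | 17.4% (−3.9) |

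Across all scenarios, the extremes at 12 months are:
- censoring at stop: −0.2 (24.9 vs 25.1) to +4.2 (50.1 vs 45.9)
- deaths only: +2.6 (52.5 vs 49.9) to +8.8 (30.1 vs 21.3)
- stop counted as an event: −0.6 (10.6 vs 11.2) to −15.2 (34.8 vs 50.0).

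The last row is a limiting case, because it takes the stop itself as the last contact. A later survival contact would shrink the effect at 12 months.

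**The case against.** **Capture is not absent.** A reader might infer that follow-up records nothing but survival and that later progressions are never captured. The documents do not support that. Appendix II lists other treatment in long-term follow-up and marks imaging at the end-of-treatment visit. Section 4.9 allows record review, which could reveal a progression. Section 6.1.10 asks for every effort to document progression after discontinuation. Adverse events run for at least 30 days, and later events attributed to the drug remain reportable. This stands, but it shows only that capture is unsystematic: the 6.1.10 request sits in a note on symptomatic deterioration and has no schedule or form.

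**Bias is not automatic.** A reader might also infer that all three endpoints are biased as planned. Step 3 shows otherwise: censoring at stop, with stopping unrelated to prognosis, costs information but gives essentially no bias. An upward EFS bias needs a handling rule that the plan does not state. This also stands.

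**The upper figure is not an expectation.** The 28% is 5 of 18, chosen to sit just under the 30% discontinuation boundary in Section 7.6. That section does not limit the discontinuations to toxicity. Section 1.3 reports that no patient in the phase III everolimus trial stopped because of adverse events, although that was a different disease.

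**The endpoints are secondary and descriptive.** Section 9.1 says so, citing the small sample. With 2 of 18 event-free, the exact 95% interval is 1% to 35%, so a 9-point shift lies within sampling error. That lowers the priority. It does not remove the gap, because an avoidable systematic error adds to the imprecision.

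**Conclusion.** The gap is real. Following the plan as written leaves a named secondary objective without systematic event data for children who stop without progression. The plan fixes neither the direction nor the size of the effect:

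- **EFS, upward** if deaths or survival contacts are used while off-treatment progressions go unseen: about +2 to +9 points at 12 months, with 5% to 28% assigned an early stop and the rates assumed in step 2.
- **PFS and duration of response** are biased if stopping is related to prognosis. With the progression hazard doubled after stopping, censoring at stop overstates the 12-month figure by up to about 4 points. Otherwise there is little bias, only lost information.
- **EFS, downward** if the last-contact item in Section 6.1.13 is counted as an event. Its natural reading is a censoring date, but it is listed alongside true events.

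A reader might infer that the primary analysis is compromised. The documents do not support that: the 7/18 design and its rule of 4 or more responses do not change. At most, a child who stops before six months may lack the later scan needed to show prolonged stable disease.

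Priority is moderate: a cheap improvement to secondary endpoints, not something that must be fixed before the trial can be relied on.

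**What to change.** **Data collection (4.9, 5.3 and the Appendix II long-term column).** For each child who stops without progression, record at the existing 6-month contact:
- disease status
- dates and results of MRIs done in routine care
- date of first progression by the Section 6.1.7 criteria
- any second malignancy
- start date of any new anticancer therapy.

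**Event rules.** Count these as PFS or EFS events, and as the end of response or stable disease, where they meet the definitions.

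**Censoring (6.1.12, 6.1.13 and 9.3).** Censor event-free children at the last adequate disease assessment. State that last contact is a censoring date and not an EFS event. Without this, the added data would not settle the direction of bias.

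**Cost.** A few fields on a contact already planned, with no study-mandated scans. The drawback is that progression dates will come from routine imaging on uneven dates, so timing after treatment will be coarser than on treatment.

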5.4 Time and Events Table

(See Appendix II)

5.5 Removal of Subjects from Study

Patients can be taken off the study treatment and/or study at any time at their own request, or they may be withdrawn at the discretion of the investigator for safety, behavioral or administrative reasons. The reason(s) for discontinuation will be documented and may include:

- 5.5.1 Patient voluntarily withdraws from treatment (follow-up permitted);
- 5.5.2 Patient withdraws consent (termination of treatment and follow-up);
- 5.5.3 Patient is unable to comply with protocol requirements;
- 5.5.4 Patient demonstrates disease progression (unless continued treatment with study drug is deemed appropriate at the discretion of the investigator);
- 5.5.5 Patient experiences toxicity that makes continuation in the protocol unsafe;
- 5.5.6 Treating physician judges continuation on the study would not be in the patient's best interest;

- 5.5.7 Patient becomes pregnant (pregnancy to be reported along same timelines as a serious adverse event);
- 5.5.8 Development of second malignancy (except for basal cell carcinoma or squamous cell carcinoma of the skin) that requires treatment, which would interfere with this study;
- 5.5.9 Lost to follow-up: If a research subject cannot be located to document survival after a period of 2 years, the subject may be considered "lost to follow-up." All attempts to contact the subject during the two years must be documented and approved by the Data Monitoring Committee.

6.0 MEASUREMENT OF EFFECT

6.1 Response Assessment

6.1.1 Definitions

Evaluable for toxicity. All patients will be evaluable for toxicity from the time of their first treatment with study drug.

Evaluable for objective response. Only those patients who have measurable disease present at baseline, have received at least one cycle of therapy, and have had their disease re-evaluated will be considered evaluable for response. These patients will have their response classified according to the definitions stated below. (Note: Patients who exhibit objective disease progression prior to the end of cycle 1 will also be considered evaluable.)

In this study, response and progression will be evaluated using the International Society of Pediatric Oncology Brain, Tumor Subcommittee for the Reporting of Trials criteria shown below with slight modification.³⁴ Response will be assessed by magnetic resonance imaging (MRI) scan every 8 weeks (every 2 cycles) for 1 year, then every 12 weeks.

6.1.2 Complete Response (CR):

Complete disappearance on MRI of all enhancing tumor and mass effect, on a stable or decreasing dose of corticosteroids (or receiving only adrenal replacement doses), accompanied by a stable or improving neurologic examination and must be sustained for at least 4 weeks. If cerebral spinal fluid (CSF) evaluation was positive, it must become negative. CSF negativity has to be confirmed at least two times at consecutive samplings if the CSF was positive.

6.1.3 Partial Response (PR):

Greater than or equal to 50% reduction in tumor size by bi-dimensional measurement on a stable or decreasing dose of corticosteroids, accompanied by a stable or improving neurologic examination and must be sustained for at least 4 weeks.

6.1.4 Minor Response (MR):

Greater than or equal to 25% to < 50% reduction in tumor size by bi-dimensional measurement on a stable or decreasing dose of corticosteroids, accompanied by a stable or improving neurologic examination and must be sustained for at least 4 weeks.

6.1.5 Stable Disease (SD):

Neurologic examination is at least stable and maintenance corticosteroid dose is not increased, and MRI meets neither the criteria for MR nor the criteria for progressive disease and must be sustained for at least 8 weeks.

6.1.6 Stable Disease (SD):

Neurologic examination is at least stable and maintenance corticosteroid dose is not increased, and MRI meets neither the criteria for MR nor the criteria for progressive disease and must be sustained for at least 8 weeks.

6.1.6.1 Prolonged Stable Disease is defined as stable disease for at least 6 months duration.**6.1.7 Progressive Disease (PD):**

Progressive neurologic abnormalities or worsening neurologic status not explained by causes unrelated to tumor progression (eg, anticonvulsant or corticosteroid toxicity, electrolyte disturbances, sepsis, hyperglycemia, etc), OR a greater than 25% increase in the bi-dimensional measurement on MRI, OR the appearance of a new lesion or new CSF positivity, OR increasing doses of corticosteroids required to maintain stable neurologic status or imaging.

All patients who have measurable disease according to the above response criteria, who received at least 1 cycle of therapy and who have their disease re-evaluated will be evaluable for response. All sites of disease should be followed as either target or nontarget lesions, as categorized at baseline. All measurable lesions up to a maximum of 5 lesions should be identified as target lesions, while all other lesions (either additional measurable lesions or nonmeasurable lesions) should be classified as nontarget lesions. If possible, the same method, radiological or physical, should be employed and assessed by the same individual on each occasion. If possible, the same method should be employed and assessed by the same institution on each occasion. Ideally, any response should be confirmed by repeated evaluation at least 28 days after the first assessment where the response criteria were met.

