6.1.10 Evaluation of Best Overall Response

The best overall response is the best response recorded from the start of the treatment until disease progression/recurrence (taking as reference for progressive disease the smallest measurements recorded since the treatment started). The patient's best response assignment will depend on the achievement of both measurement and confirmation criteria.

Table 6-1

Target Lesions	Non-Target Lesions	New Lesions	Overall Response	Best Response for this Category Also Requires:
CR	CR	No	CR	>4 wks. confirmation
CR	Non-CR/Non-PD	No	PR	>4 wks. confirmation
PR	Non-PD	No	PR	
SD	Non-PD	No	SD	documented at least once >4 wks. from baseline
PD	Any	Yes or No	PD	no prior SD, PR or CR
Any	PD*	Yes or No	PD	
Any	Any	Yes	PD	

* In exceptional circumstances, unequivocal progression in non-target lesions may be accepted as disease progression.

Note: Patients with a global deterioration of health status requiring discontinuation of treatment without objective evidence of disease progression at that time should be reported as "*symptomatic deterioration*". Every effort should be made to document the objective progression even after discontinuation of treatment.

Note: If subjects respond to treatment and are able to have their disease resected, the patient's response will be assessed prior to the surgery.

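### Section 9.2 counts responders among accrued patients, 6.1.1 and 6.1.7 admit only re-evaluated patients, and 9.3 does not say which set the ORR uses; the evaluable set can only equal or raise it.

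*Combined protocol and SAP*

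**What the plan says.** Section 6.1.1 limits response evaluation to patients with measurable disease at baseline who "have received at least one cycle of therapy, and have had their disease re-evaluated will be considered evaluable for response". It adds one group back: "Patients who exhibit objective disease progression prior to the end of cycle 1 will also be considered evaluable". Section 6.1.7 repeats the restriction for those "who received at least 1 cycle of therapy and who have their disease re-evaluated will be evaluable for response". No other response population is defined.

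Section 9.2 is written in terms of accrual. Seven patients are accrued and the study stops if none of them responds. Otherwise 11 more are accrued, and the null ORR of 10% is rejected if 4 or more of the 18 respond. The stated type I error is 10%, and the stated power is 80% at a true ORR of 30%. Section 9.2 does not refer to 6.1.1 or say how an accrued patient without a re-evaluation is counted. Section 9.3 specifies the exact binomial method and a 95% interval and names no analysis set.

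For safety the plan is explicit. Section 6.1.1 says "All patients will be evaluable for toxicity from the time of their first treatment with study drug", and 6.2 says "Analyses will be performed for all patients having received at least one dose of study drug".

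Two sections provide for replacement. Section 4.11 allows a patient to be added when someone withdraws before completing one course without a DLT. Section 6.1.9 requires replacement when a patient is removed because central review disagrees with the local read, even if study drug has been started. Neither says whether the replaced patient stays in the efficacy count.

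**The concern.** ORR is the primary endpoint. An analyst following 9.2 would divide by 18, while one following 6.1.1 would divide by a smaller number. The excluded patients are not a random subset. They are treated patients who leave because of toxicity, withdrawal, death or clinical decline before any re-evaluation and without documented progression. The first scheduled MRI on treatment is before course 3, at about week 8 (5.2.2), so there is time for this to happen. CR and PR must be sustained for at least 4 weeks, and prolonged stable disease must last at least 6 months, so none of these patients could be a documented success. Leaving them out moves the estimate in one direction only. With the denominator unsettled, the choice could also be made after the results are known.

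**Working it through.** **Inputs.** From 9.2: null ORR 0.10, alternative 0.30, stage 1 of 7 with a stop at 0 responders, total 18, rejection at 4 or more. From 9.3: exact binomial interval. The documents give no non-evaluable rate for this trial; the 5% and 10% used below are assumptions.

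**Step 1: reproduce the design.** The probability of rejection is the sum over x = 1 to 7 of P(X1 = x; 7, p) × P(X2 ≥ 4 − x; 11, p).

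| Stage 1 responders | p = 0.10 | p = 0.30 |
|---|---|---|
| 1 | 0.3720 × 0.0896 = 0.0333 | 0.2471 × 0.6873 = 0.1698 |
| 2 | 0.1240 × 0.3026 = 0.0375 | 0.3177 × 0.8870 = 0.2818 |
| 3 | 0.0230 × 0.6862 = 0.0158 | 0.2269 × 0.9802 = 0.2224 |
| 4 or more | 0.0027 | 0.1260 |
| Total | 0.0893 | 0.8000 |

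The design reproduces: 10% is the nominal ceiling, 0.089 is attained, and power is 0.800.

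**Step 2: direction of the shift.** Let r be the number of responders, 18 the number treated and k the number excluded as never re-evaluated. All k are non-responders, so the two estimates are r/18 and r/(18 − k). The second is never smaller, and it is larger whenever r ≥ 1 and k ≥ 1.

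**Step 3: size of the shift.**

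| Responders | All 18 | One excluded (17) | Two excluded (16) | Rise, points |
|---|---|---|---|---|
| 1 | 5.6% | 5.9% | 6.3% | 0.3 to 0.7 |
| 4 | 22.2% | 23.5% | 25.0% | 1.3 to 2.8 |
| 8 | 44.4% | 47.1% | 50.0% | 2.6 to 5.6 |

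With 4 responders the exact 95% intervals are 6.4 to 47.6% (4/18), 6.8 to 49.9% (4/17) and 7.3 to 52.4% (4/16). With no responders there is no shift.

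**Step 4: the decision.** The 9.2 rule is a count of responders. Excluding non-responders without replacing them leaves that count, and so the decision, unchanged.

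**Step 5: what happens if patients are added.** Suppose all treated patients stay in the count, additions take the total N above 18, and the cutoff stays at 4. Replacing 11 by N − 7 in the step 1 formula gives a type I error of 0.103 at N = 19 and 0.117 at N = 20. One added patient is enough to pass the stated 10%.

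**Step 6: if the planned rates refer to evaluable patients.** Counting everyone treated then lowers the effective rate to p(1 − q), where q is the non-evaluable share. At q = 5%, 0.30 × 0.95 = 0.285 gives power 0.76. At q = 10%, 0.30 × 0.90 = 0.270 gives power 0.72. Under the null, 0.095 and 0.090 give a type I error of 0.077 and 0.066.

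**The case against.** The strongest reply is that 9.2 already names its patients: the 7 and the 18 are those accrued, and the word evaluable does not occur there. That stands. A reader might infer that the plan has no denominator at all, or that the stage 1 rule is undefined; the text of 9.2 supports neither. What remains is that 9.2 is not reconciled with 6.1.1 and 6.1.7, and that 9.3 chooses neither for the reported rate and interval.

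A second reply is that few patients would be lost. Objective progression in cycle 1 keeps a patient in. Section 6.1.7 counts unexplained neurologic worsening and "increasing doses of corticosteroids required to maintain stable neurologic status or imaging" as progression. Section 5.2.2 allows MRI when clinically indicated, and Appendix II marks an MRI at the end-of-treatment visit. Section 6.1.10 says "Every effort should be made to document the objective progression even after discontinuation of treatment". These provisions shrink the excluded group but do not empty it. Section 6.1.10 itself foresees "Patients with a global deterioration of health status requiring discontinuation of treatment without objective evidence of disease progression at that time", and 5.5.2 ends follow-up when consent is withdrawn.

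A third reply is that the effect is small against an interval about 41 points wide, in a study that 9.1 says will be reported descriptively. That is fair and limits the weight of the point.

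A stronger inference is that the evaluable-only rule inflates the type I error. Exclusion alone does not. Replacing every non-evaluable patient would do so if 10% is the null rate among all treated: at 5% non-evaluable the rate per counted patient is 0.10/0.95 = 0.105 and the type I error 0.103; at 10% it is 0.10/0.90 = 0.111 and 0.120. The documents do not say that 10% is an all-treated rate. Section 4.11 covers only withdrawals before the end of course 1 without a DLT, and 6.1.9 only disagreements at central review. If 10% is the rate among evaluable patients, the error stays at 0.089.

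**Conclusion.** The point holds as a failure to reconcile sections, with a bias of known direction. An ORR reported on the 6.1.1 set can only equal or exceed the all-treated ORR. Near the decision boundary of 4 responders the rise is 1.3 points with one patient excluded and 2.8 with two; it is smaller with fewer responders and larger with more. The direction rests only on the response definitions. The size depends on how many patients go unassessed, which the documents do not give. Under assumed non-evaluable rates of 5% and 10%, the chance of at least one such patient among 18 is 1 − 0.95^18 = 60% and 1 − 0.90^18 = 85%. The design figures in 9.2 are sound. This should be fixed because it concerns the primary endpoint and costs little, but it does not threaten the go/no-go rule.

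**What to change.** In 9.2 and 9.3, state the following.

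- The stage 1 count, the final count and the exact interval use the first 7 and the first 18 eligible patients who took at least one dose. Patients without a re-evaluation count as non-responders.
- The evaluable-only rate under 6.1.1 is a sensitivity result, reported with the number excluded and the reasons.
- An eligible treated patient who is replaced under 4.11 stays in the count, and the decision rests on the first 18 such patients. Anyone added beyond 18 is reported descriptively, or the cutoff is restated for the larger number.
- For 6.1.9, only patients found ineligible on central review of the baseline MRI leave the efficacy count. Patients removed after disagreement on a later scan stay in.
- Whether the 10% and 30% rates refer to all treated or to evaluable patients.

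If the rates are all-treated rates, this is a change of wording: type I error 0.089 and power 0.80 are kept, provided the decision stays on 18 patients. The reported ORR may be slightly lower. If the 30% was meant for evaluable patients, power falls to about 0.76 or 0.72 at an assumed 5% or 10% non-evaluable. That loss should be stated rather than met by enrolling more patients.
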